	
summarized by ATC class and preferred term using frequency distributions. Duration (days) of exposure to study drugs will be summarized using descriptive statistics separately for everolimus and exemestane.
 
Safety and tolerability
 
• Data collected by AE CRFs will be coded using the MedDRA dictionary. The incidence of treatment-emergent adverse events (new or worsening from baseline) will be summarized by MedDRA system organ class and preferred term using frequency distributions. Additionally, AE will be summarized by maximum severity (based on CTCAE grades), and for AE with suspected drug relation, serious AE (SAE), and AE leading to permanent discontinuation of study drug. All information pertaining to AE noted during the study will be listed by patient, detailing the verbatim term given by the investigator, MedDRA preferred term and system organ class, start/end dates, severity, seriousness, relationship to study drug and action taken.• The AE onset will also be shown relative (in number of days) to the date of initial dose. AE starting more than 30 days after discontinuation of study drug will not be considered as treatment-emergent and will not be included in AE summary tables but listed only.• Data from other tests (e.g., electrocardiogram or vital signs) will be summarized descriptively as appropriate. Notable values will be flagged, and any other information collected will be listed as appropriate. 
Efficacy
 
• Disease progression will be assessed based on radiological assessments of tumor burden will be derived using local radiologist's/ investigator's assessment. If a patient has not had an event at end of the study, his or her data will be censored at the date of last adequate tumor assessment.• The best overall response rate (ORR, according to RECIST 1.1) as well as individual response categories (CR, PR, SD, PD or unknown) will be summarized using frequency tables together with their associated two-sided exact 95% confidence intervals (Clopper-Pearson method).• The clinical benefit rate (CBR) is defined as the proportion of patients with best overall response of complete response (CR), partial response (PR) or stable disease (SD), with duration of 24 weeks or longer. The duration of best overall response is assessed as such: the start date is the date of first documented response (CR or PR) and the end date is the date of event defined as first documented progression disease or death due to underlying cancer. The CBR will be summarized using frequency tables together with its associated two-sided exact 95% confidence intervals (Clopper-Pearson method).• The progression-free survival (PFS) rate is defined as the proportion of patients who have not had any documented progression or death due to any cause, according to RECIST (version 1.1). If a patient has not had an event, progression-free survival is censored at the date of last adequate tumor assessment. PFS will be summarized using the Kaplan-Meier method. Percentiles (25%, median, 75%) of the event time distribution will be presented along with their two-sided 95% confidence interval. The Kaplan-Meier curve will be displayed graphically. 
Other assessments
 
• The ECOG Performance Status will be summarized using frequency distributions by visit. Shifts from baseline value to worst post-baseline value will be summarized using frequency distributions. 
[REDACTED]

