3.2.1 Secondary endpoints

Efficacy endpoints based on radiological (and photographic when applicable) assessments of tumor burden will be derived using local (treating center's) radiologist's/ investigator's assessment.

For patients without event at the end of the study, data will be censored at the date of last adequate tumor assessment.

- Overall Response Rate (ORR) over the study period:
 - Overall response rate (ORR) is defined as the proportion of patients with best overall response of either complete response (CR) or partial response (PR) according to RECIST (version 1.1).
- Progression Free Survival (PFS) rate over the study period:
 - PFS rate is defined as the proportion of patients who have not had any documented progression or death due to any cause, according to RECIST (version 1.1).
- Clinical Benefit Rate (CBR) over the study period:
 - CBR rate is defined as the proportion of patients with best overall response of complete response (CR), partial response (PR) or stable disease (SD), with duration of 24 weeks or longer, according to RECIST (version 1.1).

For these three outcomes, in patients with non-measurable disease (bone metastases), the following is considered a disease progression: appearance of one or more new bone lytic lesions; appearance of one or more lesions outside of bone; unequivocal progression of existing bone lesions. Pathological fracture, new compression fracture, or complications of bone metastases will not be considered as evidence of disease progression unless one of the above criteria is fulfilled.

Changes from baseline in ECOG performance status will be described. Time to deterioration of ECOG performance status, from baseline will be assessed.

[figure not shown]
[figure not shown]
[figure not shown]
[figure not shown]

Table 3-1 Objectives and related endpoints

Objective	Endpoint	Analysis
Primary		
To evaluate the safety and tolerability profile of everolimus in post-menopausal women with HR positive, HER2 negative locally advanced or metastatic breast cancer after documented recurrence or progression following a non-steroidal aromatase inhibitor therapy in Novartis Oncology EGM countries.	Incidence of adverse events (AEs) by grade, serious adverse events (SAEs), changes from baseline in vital signs and laboratory results (hematology, blood chemistry, lipid profile) qualifying as AEs. All AEs will be assessed according to the Common Terminology Criteria (CTCAE), version 4.03.	Refer to Section 10.5

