7.1 Study flow and visits schedule

[Table 7-1](#) lists all study assessments by visit. All data obtained from these assessments must be supported in the patient's source documentation. All assessments will be captured in the CRF, with the only exception of safety laboratory tests and ECG, which will remain only in the patient's source documents.

Tests, procedures and visits should occur on schedule as far as possible.

[figure not shown]
[figure not shown]
[figure not shown]

Table 7-1 Schedule of assessments

[figure not shown]
	Screening Day -21 to -1	Baseline Day 1	Week 4 ± 1 week	Week 10 ± 2 weeks	Week 20 ± 2 weeks	Week 30 ± 2 weeks	Week 40 ± 2 weeks	Week 50 ± 2 weeks/ EOT	Following visits (each 10 ± 2 weeks)	EOT	Follow-up EOT + 30 days (± 2 days)
Visit N°	1	2	3	4	5	6	7	8	N	EOT	F-up
Informed consent	X										
Demographics	X										
Eligibility criteria	X	X									
Medical history, current medical conditions	X										
Diagnosis and extent of breast cancer	X										
Prior antineoplastic therapies	X										
Height, weight	X										
Physical examination	X	X	X	X	X	X	X	X	X	X	
Vital signs, ECOG status	X	X	X	X	X	X	X	X	X	X	
Prior medications	X										
Concomitant medications	X	X	X	X	X	X	X	X	X	X	X
Adverse events	X	X	X	X	X	X	X	X	X	X	X
Study drugs dispensation		X	X	X	X	X	X	X	X		
CT scan/MRI chest, abdomen,	X			X	X	X	X	X	X	X	

	Screening Day -21 to -1	Baseline Day 1	Week 4 ± 1 week	Week 10 ± 2 weeks	Week 20 ± 2 weeks	Week 30 ± 2 weeks	Week 40 ± 2 weeks	Week 50 ± 2 weeks/ EOT	Following visits (each 10 ± 2 weeks)	EOT	Follow-up EOT + 30 days (± 2 days)
Visit N°	1	2	3	4	5	6	7	8	N	EOT	F-up
pelvis (1)											
Brain CT scan or MRI (2)	X	As clinically indicated									
Bone scan/ X-ray (3)	X	If bone metastases are present at baseline, a bone scan or skeletal survey is required every 10 weeks. If bone metastases are not identified at baseline, bone scans will be performed as clinically indicated									
Bone CT/MRI (3)	X	If bone metastases are present at baseline, a bone scan or skeletal survey is required every 10 weeks. If bone metastases are not identified at baseline, bone CT/MRI will be performed only to confirm potential findings identified by bone scans/X-rays.									
Hematology, chemistry, lipid profile (5)	X	X	X	X	X	X	X	X	X	X	
Hepatitis B viral load and markers	X	Monitor approximately every 3-6 weeks when required.									
Hepatitis C viral load and markers	X	Monitor approximately every 6 weeks when required.									

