10.6.1.2 Clinical benefit rate

The clinical benefit rate (CBR) will be provided over the study period. CBR rate is defined as the proportion of patients with best overall response of complete response (CR), partial response (PR) or stable disease (SD), with duration of 24 weeks or longer, according to RECIST 1.1. The best overall response for each patient is determined from the sequence of investigator overall lesion responses according to RECIST 1.1. To be assigned a best overall response of CR or PR, two determinations of CR at least 4 weeks apart before progression are required.

[figure not shown]
The duration of best overall response is assessed as such: the start date is the date of first documented response (CR or PR) and the end date is the date of event defined as first documented progression disease or death due to underlying cancer.

The CBR measured at approximately week 20 and week 50 will be summarized using frequency tables together with its associated two-sided exact 95% confidence intervals (Clopper-Pearson method).

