Overall Response rate, overall study period	n(%)	(95% CI)	n(%)	(95% CI)	n(%)	(95% CI)
Best overall response rate ^a	xxx		xxx		xxx	
Complete Response (CR)	xx (x.x)	(xx.x, xx.x)	xx (x.x)	(xx.x, xx.x)	xx (x.x)	(xx.x, xx.x)
Partial Response (PR)	xx (x.x)	(xx.x, xx.x)	xx (x.x)	(xx.x, xx.x)	xx (x.x)	(xx.x, xx.x)
Stable Disease (SD)	xx (x.x)	(xx.x, xx.x)	xx (x.x)	(xx.x, xx.x)	xx (x.x)	(xx.x, xx.x)
Progressive Disease (PD)	xx (x.x)	(xx.x, xx.x)	xx (x.x)	(xx.x, xx.x)	xx (x.x)	(xx.x, xx.x)
Unknown (UNK)	xx (x.x)	(xx.x, xx.x)	xx (x.x)	(xx.x, xx.x)	xx (x.x)	(xx.x, xx.x)
Overall Response Rate (ORR: CR+PR) ^b	xx (x.x)	(xx.x, xx.x)	xx (x.x)	(xx.x, xx.x)	xx (x.x)	(xx.x, xx.x)
Clinical Benefit Rate (CBR: CR+PR+SD >= 24 weeks) ^c	xx (x.x)	(xx.x, xx.x)	xx (x.x)	(xx.x, xx.x)	xx (x.x)	(xx.x, xx.x)
Overall Response rate, at Week 20	n(%)	(95% CI)	n(%)	(95% CI)	n(%)	(95% CI)
Best overall response rate ^a	xxx		xxx		xxx	
Complete Response (CR)	xx (x.x)	(xx.x, xx.x)	xx (x.x)	(xx.x, xx.x)	xx (x.x)	(xx.x, xx.x)
Partial Response (PR)	xx (x.x)	(xx.x, xx.x)	xx (x.x)	(xx.x, xx.x)	xx (x.x)	(xx.x, xx.x)
Stable Disease (SD)	xx (x.x)	(xx.x, xx.x)	xx (x.x)	(xx.x, xx.x)	xx (x.x)	(xx.x, xx.x)
Progressive Disease (PD)	xx (x.x)	(xx.x, xx.x)	xx (x.x)	(xx.x, xx.x)	xx (x.x)	(xx.x, xx.x)
Unknown (UNK)	xx (x.x)	(xx.x, xx.x)	xx (x.x)	(xx.x, xx.x)	xx (x.x)	(xx.x, xx.x)
Overall Response Rate (ORR: CR+PR) ^b	xx (x.x)	(xx.x, xx.x)	xx (x.x)	(xx.x, xx.x)	xx (x.x)	(xx.x, xx.x)
Clinical Benefit Rate (CBR: CR+PR+SD >= 24 weeks) ^c	xx (x.x)	(xx.x, xx.x)	xx (x.x)	(xx.x, xx.x)	xx (x.x)	(xx.x, xx.x)
Overall Response rate, at Week 50	n(%)	(95% CI)	n(%)	(95% CI)	n(%)	(95% CI)
Best overall response rate ^a	xxx		xxx		xxx	
Complete Response (CR)	xx (x.x)	(xx.x, xx.x)	xx (x.x)	(xx.x, xx.x)	xx (x.x)	(xx.x, xx.x)
Partial Response (PR)	xx (x.x)	(xx.x, xx.x)	xx (x.x)	(xx.x, xx.x)	xx (x.x)	(xx.x, xx.x)
Stable Disease (SD)	xx (x.x)	(xx.x, xx.x)	xx (x.x)	(xx.x, xx.x)	xx (x.x)	(xx.x, xx.x)
Progressive Disease (PD)	xx (x.x)	(xx.x, xx.x)	xx (x.x)	(xx.x, xx.x)	xx (x.x)	(xx.x, xx.x)
Unknown (UNK)	xx (x.x)	(xx.x, xx.x)	xx (x.x)	(xx.x, xx.x)	xx (x.x)	(xx.x, xx.x)
Overall Response Rate (ORR: CR+PR) ^b	xx (x.x)	(xx.x, xx.x)	xx (x.x)	(xx.x, xx.x)	xx (x.x)	(xx.x, xx.x)
Clinical Benefit Rate (CBR: CR+PR+SD >= 24 weeks) ^c	xx (x.x)	(xx.x, xx.x)	xx (x.x)	(xx.x, xx.x)	xx (x.x)	(xx.x, xx.x)

Asian: Indonesia, India, Vietnam, Turkey, South Korea, Thailand, Malaysia, Taiwan or Jordan.

Non-Asian: Australia, Morocco, South Africa or Tunisia.

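### A Week 20 clinical benefit rate cannot count stable disease on Week 20 data and otherwise largely overlaps the study-period rate; separately, 10.6.1.2 misstates the PR rule

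*Protocol*

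**What the plan says.** **Endpoint and time points.** Protocol 3.2.1 sets the secondary endpoint as "Clinical Benefit Rate (CBR) over the study period". Section 10.6.1.2 adds two time points: "The CBR measured at approximately week 20 and week 50 will be summarized using frequency tables". The CBR sentence in the protocol summary has none: "The CBR will be summarized using frequency tables together with its associated two-sided exact 95% confidence intervals (Clopper-Pearson method".

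**SAP shell.** Table 8.1.1 has three blocks: "Overall Response rate, overall study period", "Overall Response rate, at Week 20" and a Week 50 block. Each contains a CBR row labelled as CR plus PR plus SD of at least 24 weeks. Footnote c accepts CR and PR of any duration and applies the 24 weeks to SD only. Table 8.1.2 and subgroup tables S1.8.1.1 to S4.8.1.1 reuse the layout.

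**Clock.** Appendix 14.1.22 and SAP Table 8.2.1 footnote c start SD duration at the start of treatment. The only clock in 10.6.1.2 starts at the first CR or PR.

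**Schedule.** Table 7-1 places the scans at "Week 20 ± 2 weeks" and then "Week 30 ± 2 weeks". Section 7.1 adds: "Tests, procedures and visits should occur on schedule as far as possible".

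**PR rule.** Section 10.6.1.2 asks for two CRs, four weeks or more apart, before either CR or PR is assigned. Section 10.6.1.1, Appendix 14.1.16 (where confirmation is required) and SAP Table 8.1.1 footnote a ask only for two assessments of PR or better to confirm a PR.

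**The concern.** A reader who sees a Week 20 CBR with an exact confidence interval will take it as the share of patients with disease control at that point, stable disease included. The 24-week requirement runs past the end of the visit window, so on Week 20 data the SD component is empty while the row label still names it. Neither document says whether later scans are to be used. What is at stake is a mislabelled or redundant row, repeated across the main, per-protocol and subgroup tables.

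The PR sentence in 10.6.1.2 is a separate matter. A patient with two CRs is a CR, so a rule that demands two CRs leaves nobody to be called PR. The same patient could then be a PR for ORR and not for CBR.

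**Working it through.** The plan states no figure to reproduce. The check is date arithmetic on the visit windows, plus a comparison of the definitions.

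**Inputs.** Threshold 24 weeks (10.6.1.2; SAP Table 8.1.1 footnote c). SD clock from treatment start (Appendix 14.1.22; SAP Table 8.2.1 footnote c). Windows of ±2 weeks at Weeks 10, 20, 30 and 50 (Table 7-1). Duration in days = end − start + 1 (Appendix 14.1.33).

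**1. Longest SD visible at an on-schedule Week 20 visit.** 20 + 2 = 22 weeks, and 24 − 22 = 2 weeks short. In days, 22 × 7 + 1 = 155, against 24 × 7 = 168. Only a visit at least 2 weeks outside its window could reach the threshold.

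**2. Row built from data up to Week 20.**
- Footnote c (CR and PR at any duration): CBR = CR + PR + 0 = Week 20 ORR. Confirmed responses are possible by then, because the shortest gap between the Week 10 and Week 20 scans is 18 − 12 = 6 weeks, more than 4.
- 24 weeks also required of CR and PR: the earliest scheduled scan is week 10 − 2 = 8, so the longest response is 22 − 8 = 14 weeks. Even a clock started at treatment gives only 22. The row is zero by construction. With the planned maximum of 400 patients, 0/400 would print with an exact upper limit of 1 − 0.025^(1/400) = 0.9%.

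**3. Row built with later scans.** The next scheduled on-treatment scan is no earlier than 30 − 2 = week 28, which is past 24. A patient with SD at Week 20 who goes on to that scan has therefore passed the threshold. She could still fail through:
- death before week 24;
- PD before week 24 on an unscheduled scan or an end-of-treatment scan (Tables 7-1 and 7-2 require an end-of-treatment scan);
- censoring before week 24.

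The documents give no rate for these. Otherwise the row counts the same patients as the study-period CBR, apart from those with no evaluable scan by Week 20.

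**4. Week 50.** 50 − 2 = 48 weeks, above 24, so the Week 50 CBR is attainable. The study-period CBR has no cut at all.

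**5. Extent.** Tables 8.1.1, 8.1.2, S1.8.1.1, S2.8.1.1, S3.8.1.1 and S4.8.1.1 make 6 tables; 6 × 3 columns = 18 column entries.

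**6. PR rule.** Take PR at Weeks 10 and 20 and PD at Week 30. Section 10.6.1.1 gives a confirmed PR. The literal rule in 10.6.1.2 denies PR; if the patient falls back to SD, her duration is 30 − 0 = 30 weeks and she still counts in the study-period CBR. The rate therefore moves little, even if the literal rule were programmed.

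**7. Scope of the 24 weeks.** The same patient has a response lasting 30 − 10 = 20 weeks on the clock in 10.6.1.2. She counts under footnote c, but would not if the 24 weeks covered responses.

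**The case against.** The strongest reply is that nothing proves a data cut at Week 20. The SAP runs SD duration to progression with no truncation, and records best response until progression. The main analysis is planned at 15 months of median follow-up, when later scans exist. On that reading the row does contain SD patients and is merely redundant. This stands. A reader might infer that the Week 20 row must show zero SD patients, but that holds only if the row uses data up to an on-schedule visit. The programmer note on Week 20 and Week 50 CRF data does not settle it, because it sits under the whole table, study-period block included. The defect is an undefined row, not a proven zero. The word approximately in 10.6.1.2 does not rescue the row either: the stated tolerance ends at week 22 and the next scheduled scan is at week 28 at the earliest.

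On the PR rule, the SAP shell uses one best-response classification for both ORR and CBR, and footnote a accepts PR or better. A reader might infer that no PR will appear in the planned tables, or that programmers will split on the 24-week scope. The documents do not support that: footnotes a and c settle both points for the planned output. What remains is protocol text that is wrong or incomplete as written.

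**Conclusion.** The point holds, and it is minor. Neither way of deriving the Week 20 CBR row gives a distinct, correctly labelled clinical benefit rate. On data up to an on-schedule visit it has no SD component, and equals either the Week 20 ORR or zero. With later scans it largely overlaps the study-period CBR. How many patients the row would miss or duplicate cannot be computed, because the documents give no ORR, CBR or early-discontinuation rate for the combination. The result rests on SD being timed from treatment start and on the windows in Table 7-1.

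The PR rule in 10.6.1.2 is wrong as written and conflicts with three other places, but its effect on the planned output is small.

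A reader might go further and infer that the clinical benefit endpoint itself is compromised. It is not. The study-period CBR and the Week 50 CBR are outside the Week 20 problem, and section 10.7 states that no hypothesis will be tested.

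**What to change.** 1. Delete the CBR row from the Week 20 block of SAP Tables 8.1.1, 8.1.2 and S1.8.1.1 to S4.8.1.1, and remove the Week 20 time point from the CBR sentence in 10.6.1.2. Keep the study-period and Week 50 CBR. The protocol summary, which names no time point for CBR, needs no change.
2. Replace the PR rule in 10.6.1.2 with the one in 10.6.1.1: two assessments of PR or better, four weeks or more apart, both before progression, in a patient who does not qualify as a CR.
3. As alignment only, bring 10.6.1.2 into line with SAP Table 8.1.1 footnote c (24 weeks for SD; CR and PR at any duration), and state that SD duration starts at treatment start.

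**Cost.** One row in six SAP shells and a few sentences in 10.6.1.2, with no new data. The protocol edits need a written amendment with the approvals in section 12.1. Alternatively, they can be recorded in the analysis plan as a stated deviation, as Appendix 14.1.28 allows.

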10.6.1.3 Progression-free survival

Progression-free survival (PFS) is the time from date of start of treatment to the date of event defined as the first documented progression or death due to any cause. If a patient has not had an event, progression-free survival is censored at the date of last adequate tumor assessment.

Disease progression will be assessed using the local (treating center's radiologist's) investigator's tumor assessment. PFS will be summarized using the Kaplan-Meier method. Percentiles (25%, median, 75%) of the event time distribution will be presented along with their two-sided 95% confidence interval. The Kaplan-Meier curve will be displayed graphically.

[figure not shown]
10.6.1.4 Handling of missing data

The evaluation of overall lesion response at each assessment is a composite of the target lesion response, non-target lesion response and presence of new lesions (see Post-text supplement 1). If the evaluation of any of the target or non-target lesions identified at baseline could not be made during follow-up, the overall status must be 'unknown' unless progression was seen. Patients with a best overall response assessment of unknown (UNK) will not be regarded as 'responders' but will be included in the denominator for the calculation of the ORR for the FAS.

10.6.2 Other endpoints

10.6.2.1 ECOG Performance Status

The ECOG Performance Status will be summarized using frequency distributions by visit. Shifts from baseline value to worst post-baseline value will be summarized using frequency distributions.

10.7 Sample size calculation

No hypothesis testing will be performed in this study, which is descriptive in purpose.

The proposed sample size is up to 400 patients. The study recruitment will be globally competitive and end by October 31st 2014 at latest.

The actual sample size may differ from this plan.

[figure not shown]
11 Ethical considerations and administrative procedures

11.1 Regulatory and ethical compliance

This clinical study was designed, shall be implemented and reported in accordance with the ICH Harmonized Tripartite Guidelines for Good Clinical Practice, with applicable local regulations (including European Directive 2001/20/EC and US Code of Federal Regulations Title 21), and with the ethical principles laid down in the Declaration of Helsinki

11.2 Responsibilities of the investigator and IRB/IEC/REB

The protocol and the proposed informed consent form must be reviewed and approved by a properly constituted Institutional Review Board/Independent Ethics Committee/Research Ethics Board (IRB/IEC/REB) before study start.

Prior to study start, the investigator is required to sign a protocol signature page confirming his/her agreement to conduct the study in accordance with these documents and all of the instructions and procedures found in this protocol and to give access to all relevant data and records to Novartis monitors, auditors, Novartis Clinical Quality Assurance representatives, designated agents of Novartis, IRBs/IECs/REBs and regulatory authorities as required.

11.3 Informed consent procedures

Eligible patients may only be included in the study after providing written (witnessed, where required by law or regulation), IRB/IEC/REB-approved informed consent, or, if incapable of doing so, after such consent has been provided by a legally acceptable representative of the patient. In cases where the patient's representative gives consent, the patient should be informed about the study to the extent possible given his/her understanding. If the patient is capable of doing so, he/she should indicate assent by personally signing and dating the written informed consent document or a separate assent form. Informed consent must be obtained before conducting any study-specific procedures (i.e. all of the procedures described in the protocol). The process of obtaining informed consent should be documented in the patient source documents. The date when a subject's Informed Consent was actually obtained will be captured in their eCRFs.

Novartis will provide to investigators in a separate document a proposed informed consent form (ICF) that is considered appropriate for this study and complies with the ICH GCP guideline and regulatory requirements. Any changes to this ICF suggested by the investigator must be agreed to by Novartis before submission to the IRB/IEC/REB, and a copy of the approved version must be provided to the Novartis monitor after IRB/IEC/REB approval.

